7.1.1. Analysis of demographics

Demographic characteristics (age at the first dose in years, gender and race), cohort description and other characteristics such as smoking/exposure history status, pulmonary function test baseline results, height, weight and previous vaccination with a pneumococcal vaccine or an influenza vaccine will be summarized by group using descriptive statistics:

- Frequency tables will be generated for categorical variables such as race;
- Mean, median and standard deviation will be provided for continuous data such as age.
- The distribution of subjects enrolled among the study sites will be tabulated as a whole and per group.
- Withdrawal status will be summarised by group using descriptive statistics:
 - The numbers of withdrawn subjects will be tabulated according to the reason for withdrawal.
- The number of subjects enrolled into the study as well as the number of subjects excluded from ATP analyses will be tabulated.

7.1.2. Analysis of safety

The primary analysis will be performed on the TVC and, if in any vaccine group and at any time point the percentage of vaccinated subjects excluded from the ATP cohort is at least 10%, a second analysis will be performed on the ATP cohort to complement the TVC.

The percentage of subjects with at least one local AE (solicited and unsolicited), with at least one general AE (solicited and unsolicited) and with any AE during the 7-day or 30-day follow-up period will be tabulated after Dose 1 and Dose 2 and overall with exact 95% CI. The same computations will be done for Grade 3 AEs, any AEs causally related to vaccination and any Grade 3 AEs causally related to vaccination.

The percentage of subjects/doses reporting each individual solicited local (any grade, Grade 3) and general (any grade, Grade 3, any causally related to vaccination and any Grade 3 causally related to vaccination) AE during the 7-days (Day 0 to Day 6) follow-up period will be tabulated for each group as follows:

- Overall, the percentage of subjects with the symptom and its exact 95% CI.
- Overall, the percentage of doses with the symptom and its exact 95% CI.
- At each study dose (visit), the percentage of subjects with the symptom and its exact 95% CI.

Statistical Analysis Plan

Study alias & e-track number(s): NTHI MCAT-001 (201281)

The exact 95% CIs will be calculated assuming independence between doses. For fever, additional analyses will be performed by 0.5°C increments.

The verbatim reports of **unsolicited symptoms** will be reviewed by a physician and the signs and symptoms will be coded according to the MedDRA Dictionary for Adverse Reaction Terminology. Every verbatim term will be matched with the appropriate preferred term (PT). The percentage of subjects with unsolicited symptoms within 30 days after any doses with its exact 95% CI will be tabulated by group and by MedDRA PT. Similar tabulation will be done for Grade 3 unsolicited symptoms, for unsolicited symptoms that resulted in a medically attended visit, for unsolicited symptoms causally related to vaccination and for Grade 3 symptoms causally related to the vaccination.

For each group and for each **haematology and biochemistry parameter**:

- The percentage of subjects having haematology and biochemistry results below or above the normal laboratory ranges will be tabulated by time point.
- The maximum grading from Screening up to Visit 6 (Day 90) will be tabulated (grades will be based on local laboratory normal ranges and derived from FDA Guidance to Industry “Toxicity Grading Scale for Healthy Adult and Adolescent Volunteers Enrolled in Preventive Vaccine Clinical Trials”. Those laboratory parameters not included in the FDA grading scale will not be graded).

The number of subjects who experienced at least one SAE or any pIMDs from first vaccination up to 30 days post-Dose 2 will be reported.

The percentage of subjects/dose using **concomitant medication/ product** (any medication/ product, any antipyretic and any antipyretic taken prophylactically, respectively) during the 30-day follow-up period (Day 0 – Day 29) will be summarised per group for each dose and overall per dose.

The number of subjects who experienced any **AE leading to study withdrawal, or any SAE related to study participation or concurrent GSK medication/ vaccination**, from first vaccination up to 30 days post-Dose 2 will be reported.

Pregnancy reports from first vaccination up to 30 days post-Dose 2 and pregnancy outcomes will be described in detail.

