1.2.3. Rationale for the use of placebo

The placebo group (saline solution) is included in the NTHI MCAT-001 study as a control for both safety and immunogenicity assessments.

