5.2.2.2.1. Study group and treatment number allocation

The target will be to enrol approximately 120 eligible subjects who will be randomly assigned per step:

- **Step 1:** two study groups in a (1:1) ratio (approximately 15 subjects per group).
- **Step 2:** three study groups in a (1:1:1) ratio (approximately 30 subjects per group).

Allocation of the subject to a study group at the investigator site will be performed using SBIR.

Subjects will be minimised for centre at Step 1. At Step 2, subjects will be minimised for age (50-59 years or 60-70 years), for smoking status (current or former smokers), for centre and for forced expiratory volume in 1 second (FEV₁) / forced vital capacity (FVC) (≥ 0.7 or < 0.7). Minimisation factors will have equal weight in the minimisation algorithm.

As several minimisation factors have been defined for the treatment allocation at Step 2, it was decided at the design phase not to minimise for the CMI group allocation. This wouldn't be feasible from an implementation point of view. (Amended 16 March 2016)

After obtaining the signed and dated ICF from the subject (at Screening Visit) and after having checked the eligibility of the subject, the dedicated study staff will access SBIR (at Visit 1). Upon providing the information for each minimisation factor and the subject identification number, the randomisation system will determine the study group and will provide the treatment number to be used for the first dose. This treatment number will be used by the dedicated staff member for administration of the vaccine.

The number of each administered treatment must be recorded in the eCRF on the Vaccine Administration screen.

When SBIR is not available, please refer to the SBIR user guide or the Study Procedures Manual (SPM) for specific instructions.

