10.3. Determination of sample size

[figure not shown]
This study is a Phase I safety study to get a preliminary safety assessment of the vaccine formulations in healthy adults.

Considering the sample size of 15 in each study group in Step 1, [Table 23](#) illustrates the precision one can get on the percentage of subjects with symptoms following vaccination.

Table 23 Exact confidence interval for one proportion with 15 subjects

| Number(%) of subjects with a symptom | Exact 95% Confidence Interval (CI) | |
|--------------------------------------|------------------------------------|-------------|
| | Lower Limit | Upper limit |
| 0 (0.0) | 0.0 | 21.8 |
| 1 (6.7) | 0.2 | 31.9 |
| 2 (13.3) | 1.7 | 40.5 |
| 3 (20.0) | 4.3 | 48.1 |
| 4 (26.7) | 7.8 | 55.1 |
| 5 (33.3) | 11.8 | 61.6 |
| 6 (40.0) | 16.3 | 67.7 |
| 7 (46.7) | 21.3 | 73.4 |
| 8 (53.3) | 26.6 | 78.7 |
| 9 (60.0) | 32.3 | 83.7 |
| 10 (66.7) | 38.4 | 88.2 |
| 11 (73.3) | 44.9 | 92.2 |
| 12 (80.0) | 51.9 | 95.7 |
| 13 (86.7) | 59.5 | 98.3 |
| 14 (93.3) | 68.1 | 99.8 |
| 15 (100.0) | 78.2 | 100 |

Considering the sample size of 30 or less in each study group in Step 2, [Figure 5](#) illustrates the probability of detecting an AE with a true occurrence rate of 0 - 10%.

Figure 5 Probability of not detecting an AE with a true occurrence rate of 0-10%

The probability of detecting an AE with a true incidence of 5% is around 78.5% with 30 subjects per group.

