7.2.2. Analysis of safety

The primary analysis will be performed on the TVC and, if in any vaccine group and at any time point the percentage of vaccinated subjects excluded from the ATP cohort is at least 10%, a second analysis will be performed on the ATP cohort to complement the TVC.

Study alias & e-track number(s): NTHI MCAT-001 (201281)

The percentage of subjects with at least one **local AE** (solicited and unsolicited), with at least one **general AE** (solicited and unsolicited) and with any AE during the 7-day or 30-day follow-up period will be tabulated after Dose 1 and Dose 2 and overall with exact 95% CI. The same computations will be done for Grade 3 AEs, any AEs causally related to vaccination and any Grade 3 AEs causally related to vaccination.

The percentage of subjects/doses reporting each individual solicited local (any grade, Grade 3) and general (any grade, Grade 3, any causally related to vaccination and any Grade 3 causally related to vaccination) AE during the 7-days (Day 0 to Day 6) follow-up period will be tabulated for each group as follows:

- Overall, the percentage of subjects with the symptom and its exact 95% CI
- Overall, the percentage of doses with the symptom and its exact 95% CI
- At each study dose (visit), the percentage of subjects with the symptom and its exact 95% CI.

The exact 95% CIs will be calculated assuming independence between doses. For fever, additional analyses will be performed by 0.5°C increments.

The verbatim reports of **unsolicited symptoms** will be reviewed by a physician and the signs and symptoms will be coded according to the MedDRA Dictionary for Adverse Reaction Terminology. Every verbatim term will be matched with the appropriate preferred term (PT). The percentage of subjects with unsolicited symptoms within 30 days after any doses with its exact 95% CI will be tabulated by group and by MedDRA PT. Similar tabulation will be done for Grade 3 unsolicited symptoms, for unsolicited symptoms that resulted in a medically attended visit, for unsolicited symptoms causally related to vaccination and for Grade 3 symptoms causally related to the vaccination.

For each group and for each **haematology and biochemistry parameter**:

- The percentage of subjects having haematology and biochemistry results below or above the normal laboratory ranges will be tabulated by time point.

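### No vaccine-versus-placebo analysis is specified for any primary safety endpoint, and the SAP presents placebo pooled across two separately randomised steps

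*SAP*

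**What the plan says.** Protocol 1.2.3 includes placebo "as a control for both safety and immunogenicity assessments". Protocol 5.2.2.2.1 randomises Step 1 equally to 10-10-10 and PLACE1, and Step 2 to "three study groups in a (1:1:1) ratio (approximately 30 subjects per group"): 10-10-10-AS, 10-10-3-AS and PLACE2.

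The primary safety analyses are in SAP Amendment 2, sections 7.1.2 (to Day 90) and 7.2.2 (to Day 420), and largely repeat protocol 10.6.2.
- Adverse event percentages "will be tabulated after Dose 1 and Dose 2 and overall with exact 95% CI".
- For unsolicited events, "The percentage of subjects with unsolicited symptoms within 30 days after any doses with its exact 95% CI will be tabulated by group" and by preferred term.
- Laboratory results are percentages outside the normal range and maximum grades, without intervals.
- SAEs and pIMDs are numbers of subjects.
- SAP 11 gives the interval method, Clopper-Pearson for a proportion within a group.

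SAP 7.1 and 7.2 say that presentation is by study group, with the placebo data of the two steps pooled. Protocol 10.6 says only that it is by study group. The group table in SAP 3 keeps separate labels for PLACE1 and PLACE2 and adds a pooled label.

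Two places point towards a comparison. Protocol 10.7 says that comparative analyses of reactogenicity and immunogenicity between groups will be descriptive. SAP 8.1 fixes the decimals for a percentage difference and its confidence limits. The only between-group analysis actually defined is the ANCOVA of antibody GMCs between the two adjuvanted groups (SAP 7.1.3.1 and 7.2.3.1).

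On sizing, protocol 10.3 states: "The probability of detecting an AE with a true incidence of 5% is around 78.5% with 30 subjects per group".

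**The concern.** Safety is the only primary objective, and the trial randomises a concurrent control for it. Headache, fatigue, myalgia, 30-day unsolicited events and out-of-range laboratory values all occur without a vaccine, and some may well be common in smokers aged 50-70. A percentage in one arm mixes that background with any vaccine effect. The quantity that separates them is the difference from the placebo group of the same randomisation, and the plan does not define it.

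Pooling adds a second problem. If the placebo column combines both steps, an adjuvanted group of older smokers stands beside a column that is one-third healthy young adults from another randomisation. If background rates differ by age and smoking, a side-by-side reading is no longer a randomised comparison.

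Protocol 10.7 treats reactogenicity and immunogenicity alike, but only the immunogenicity comparison received a method.

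**Working it through.** **1. The plan's own figure.** With n = 30 and a true rate of 5% (protocol 10.3), P(at least one event) = 1 − 0.95^30 = 0.7854. The stated 78.5% is reproduced. It uses only n and the rate in one group, so a placebo group of 30 with a 5% background gives the same value. Figure 5 has the same form: "Probability of not detecting an AE with a true occurrence rate of 0-10"%. Table 23, for Step 1, is likewise a table of one-proportion intervals.

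**2. What each text supplies for a safety contrast with placebo.**

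| Text | Groups | Endpoint | Measure and method |
|---|---|---|---|
| SAP 7.1.2, 7.2.2; protocol 10.6.2 | each group alone | all primary safety endpoints | percentage or count; exact one-proportion CI for some |
| Protocol 10.7 | not named | reactogenicity in general | descriptive; none given |
| SAP 8.1 | not named | not named | two decimals; none given |
| SAP 7.1.3.1, 7.2.3.1 | 10-10-10-AS vs 10-10-3-AS | antibody GMC | ANCOVA ratio with 95% CI |

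No row defines a vaccine-minus-placebo safety difference.

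**3. What pooling can do.** The documents give no background rates, so these are assumptions. With 15 placebo subjects at 10% (Step 1) and 30 at 30% (Step 2), the pooled rate is (15 × 0.10 + 30 × 0.30)/45 = 10.5/45 = 23.3%.
- With no vaccine effect, an AS group at 30% would appear 30 − 23.3 = 6.7 points worse than pooled placebo.
- With no vaccine effect, 10-10-10 at 10% would appear 23.3 − 10 = 13.3 points better.
- With the two rates reversed, the pooled rate is (15 × 0.30 + 30 × 0.10)/45 = 16.7% and the shifts change sign.
- With equal background rates there is no shift.

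**4. What a within-step difference would show.** The Newcombe 95% CI combines the Wilson limits (l, u) of the two groups. For d = p1 − p2, the lower limit is d − √[(p1 − l1)² + (u2 − p2)²] and the upper limit is d + √[(u1 − p1)² + (p2 − l2)²].

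| Vaccine | Placebo | Difference (points) | 95% CI |
|---|---|---|---|
| 18/30 | 9/30 | 30.0 | 4.9 to 50.4 |
| 6/30 | 2/30 | 13.3 | −4.7 to 31.3 |
| 2/30 | 0/30 | 6.7 | −5.7 to 21.3 |
| 2/30 | 2/30 | 0.0 | −15.4 to 15.4 |

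For the first row, the intervals the plan does provide are 40.6-77.3% and 14.7-49.4%. They overlap, although the interval for the difference excludes zero.

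**5. How often the interval lies above zero.** These are full binomial enumerations under assumed true rates, equal n per arm.

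| n per arm | Vaccine vs placebo | Newcombe CI above 0 | Fisher p < 0.05 |
|---|---|---|---|
| 30 | 5% vs 0% | 1.6% | 0.3% |
| 30 | 10% vs 5% | 4.9% | 1.9% |
| 30 | 60% vs 30% | 66% | 56% |
| 30 | 60% vs 20% | 90% | 85% |
| 15 | 60% vs 20% | 63% | 45% |

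Fisher power reaches 80% at 30 per arm only when the vaccine rate is about 26% against 0%, or about 36% against 5%. The differences are informative for common reactions and very imprecise for uncommon ones.

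**The case against.** The strongest reply is that this is an openly descriptive Phase I study. Protocol 10.3 calls it a preliminary safety assessment, and protocol 10.7 says that neither power nor type I error is controlled. Per-group percentages and denominators will be published, so a reader can form the difference. Related events are tabulated on blinded causality assessments, and the internal safety committee reviews the data unblinded. The SAP also has a tables annex that is not part of these documents and may contain a difference column.

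Much of this stands. The absence of a contrast breaks no stated objective, and a powered test is neither promised nor needed. But a difference with an interval is itself descriptive. A reader can form the right one only if placebo is shown by step, which the pooling sentence leaves in doubt. Committee monitoring does not define the reported analysis. An annex that sets the flow and format of tables is not where groups, endpoints and methods should first appear.

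Three stronger readings should be resisted.
- A reader might infer that the plan rules out any between-group safety comparison. Protocol 10.7 and SAP 8.1 show that one is anticipated; it is undefined.
- A reader might infer that the 78.5% is wrong or claims power against placebo. It is arithmetically right, and the sentence concerns seeing an event of a given incidence, with nothing attributed to the vaccine. Setting it beside the 0.3% or 1.6% above compares different quantities.
- A reader might treat overlap of the separate intervals as the plan's rule for comparing groups. The plan contains no such rule; the overlap in step 4 is only an illustration.

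**Conclusion.** The point holds as a gap in specification. No between-arm analysis is defined for any primary safety endpoint, and the SAP's pooled presentation can blur the within-step comparison that the randomisation supports.

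Its size depends on the event. For common reactions with differences of 30 to 40 points, 30 per arm gives an interval above zero in roughly two-thirds to nine-tenths of trials. At 5% against 0% it does so in about 2%, so the added intervals are estimates and not powered tests. All event rates here are assumptions, including those behind the pooling shifts of about 7 and 13 points, and the calculations take full groups of 15 and 30 with no loss.

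This is an inexpensive improvement to the analysis. It does not invalidate the planned tables.

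**What to change.** In SAP 7.1.2 and 7.2.2:
- Present PLACE1 and PLACE2 in separate columns for all safety tables, including laboratory results, SAEs and pIMDs. Keep pooled placebo as supplementary only, and amend the pooling sentence in 7.1 and 7.2 accordingly.
- Add, per subject, the difference in percentage with a 95% CI (for example Newcombe) for each solicited AE (any grade and Grade 3), any unsolicited AE, any Grade 3 unsolicited AE and any related AE.
- Name the contrasts: 10-10-10 minus PLACE1, 10-10-10-AS minus PLACE2, and 10-10-3-AS minus PLACE2.
- Label the intervals descriptive and unadjusted for multiplicity, as protocol 10.7 already does for comparative analyses.

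Optionally, say in protocol 10.3 that 78.5% is the probability of at least one event in one group of 30, whatever its cause. This clarifies the figure; it does not correct an error.

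The change needs no new data or subjects. The cost is programming and a larger set of unadjusted intervals: 8 solicited AEs × 2 grades + 3 other outcomes = 19 outcomes, and 19 × 3 contrasts = 57 intervals over both doses combined. Adding each dose separately would make 57 × 3 = 171. Some will exclude zero by chance and most will be wide, so the text should say that they are not tests.

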| 10-10-10 | 15 | 18 - 40 years | x | x | 1 |
| PLACE1 | 15 | 18 - 40 years | x | x | 1 |
| 10-10-10-AS | 30 | 50 - 70 years | x | x | 2 |
| 10-10-3-AS | 30 | 50 - 70 years | x | x | 2 |
| PLACE2 | 30 | 50 - 70 years | x | x | 2 |

Table 2 Study groups and treatment foreseen in the study

| Treatment name | Vaccine/ product name | Study Groups | | | | |
|----------------------------|-----------------------|--------------|-------------|------------|--------|--------|
| | | 10-10-10 | 10-10-10-AS | 10-10-3-AS | PLACE1 | PLACE2 |
| 10-10-10/Plain | NTHi-Mcat 10-10-10 | x | | | | |
| | NaCl | | | | | |
| 10-10-10/AS01 _E | NTHi-Mcat 10-10-10 | | x | | | |
| | AS01E | | | | | |
| 10-10-3/AS01 _E | NTHi-Mcat 30-30-10 * | | | x | | |
| | AS01E | | | | | |
| Placebo | NaCl | | | | x | x |

* Vials containing 37.5 µg, 37.5 µg and 12.5 µg of freeze-dried PD, PE-PilA and UspA2, respectively, will be diluted in three volumes of AS01_E (total of ~1875 µL). 0.5 mL will be administered.

- **Control:** Placebo control.
- **Vaccination schedules:** 0, 2 months (i.e. at Visit 1 [Day 0] and Visit 4 [Day 60]).
- **Treatment allocation:** Subjects will be allocated to a study group using a centralised randomisation system on internet (SBIR). SBIR will also be used for treatment allocation of the second dose. The randomisation algorithm will use a minimisation procedure accounting for centre at Step 1 and accounting for age (50-59 years or

60-70 years), for smoking status (current or former smokers), for centre and for forced expiratory volume in 1 second (FEV₁) / forced vital capacity (FVC) (≥ 0.7 or < 0.7) at Step 2.

- **Blinding:** Observer-blind.

Table 3 **Blinding of study epochs**

| Study Epochs | Blinding |
|--------------|----------------|
| Epoch 001 | observer-blind |
| Epoch 002 | observer-blind |

- **Sampling schedule:**
 - Blood samples for **safety** (haematology/ biochemistry) will be collected from all subjects at Screening Visit (pre-Day 0), at Visit 1 (Day 0), Visit 2 (Day 7), Visit 4 (Day 60), Visit 5 (Day 67), Visit 7 (Day 210) and at Visit 8 (Day 420).
 - Blood samples for **immunogenicity** will be collected from all subjects for humoral immunity at Visit 1 (Day 0), Visit 3 (Day 30), Visit 4 (Day 60), Visit 6 (Day 90), Visit 7 (Day 210) and at Visit 8 (Day 420), and from a sub-cohort of subjects for cell-mediated immunity (CMI) at Visit 1 (Day 0), Visit 4 (Day 60), Visit 6 (Day 90), Visit 7 (Day 210) and at Visit 8 (Day 420).

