- Laboratory evidence of clinically significant* haematological (complete blood cell count [RBC, WBC], WBC differential count [lymphocytes, neutrophils and eosinophils], platelets count or haemoglobin level) and biochemical (ALT, AST or creatinine) abnormalities.

* As the subjects are adult or elderly, current or former smokers, various pre-existing laboratory abnormalities might be detected. The investigator should use his clinical judgement to decide which ones are clinically significant.

- Acute disease and/or fever at the time of enrolment.
 - Fever is defined as temperature $\geq 37.5^{\circ}\text{C}$ for oral or axillary route. The preferred route for recording temperature will be oral.
 - Subjects with a minor illness (such as mild diarrhoea, mild upper respiratory infection) without fever may be enrolled at the discretion of the investigator.
- Current alcoholism and/or drug abuse.

Please refer to the [glossary of terms](#) for the definition of alcoholism.

- Has significant disease (including significant neurological or psychological disorders), in the opinion of the investigator, likely to interfere with the study and/or likely to cause death within the study duration.
- History of or current condition preventing intramuscular injection as bleeding or coagulation disorder.
- Malignancies within previous 5 years (excluding non-melanoma skin cancer) or lymphoproliferative disorders.
- Pregnant or lactating female.
- Female planning to become pregnant or planning to discontinue contraceptive precautions.
- Any other condition that the investigator judges may interfere with study findings.

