5. ENDPOINTS

5.1. Primary endpoints

- Occurrence of each solicited local and general AE, during a 7-day follow-up period (i.e. day of vaccination and 6 subsequent days) post-Dose 1 and post-Dose 2, in all subjects, in all vaccine groups.
- Occurrence of any unsolicited AEs, during a 30-day follow-up period (i.e. day of vaccination and 29 subsequent days) post-Dose 1 and post-Dose 2, in all subjects, in all vaccine groups.
- Occurrence of haematological and biochemical laboratory abnormalities, after vaccination, in all subjects, in all vaccine groups:
 - Any haematological (RBC, WBC and differential count, platelets count and haemoglobin level) or biochemical (ALT, AST and creatinine) laboratory abnormality on Day 7, Day 60, Day 67, Day 210 and Day 420.
- Occurrence of any SAE, occurring from first vaccination (Day 0) to study conclusion (Day 420) in all subjects, in all vaccine groups.
- Occurrence of any pIMD occurring from first vaccination (Day 0) to study conclusion (Day 420) in all subjects, in all vaccine groups.

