- The maximum grading from Screening up to Visit 8 (Day 420) will be tabulated (grades will be based on local laboratory normal ranges and derived from FDA Guidance to Industry “Toxicity Grading Scale for Healthy Adult and Adolescent Volunteers Enrolled in Preventive Vaccine Clinical Trials”. Those laboratory parameters not included in the FDA grading scale will not be graded).

The number of subjects who experienced at least one SAE or any pIMDs from first vaccination up to study conclusion will be reported.

The percentage of subjects/dose using **concomitant medication/ product** (any medication/ product, any antipyretic and any antipyretic taken prophylactically,

Study alias & e-track number(s): NTHI MCAT-001 (201281)

respectively) during the 30-day follow-up period (Day 0 – Day 29) will be summarised per group for each dose and overall per dose.

The number of subjects who experienced any AE leading to study withdrawal, or any SAE related to study participation or concurrent GSK medication/ vaccination, from first vaccination up to study conclusion will be reported.

Pregnancy reports from first vaccination up to study conclusion and pregnancy outcomes will be described in detail.

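### The planned laboratory tables do not separate new abnormalities from pre-existing ones; adding a Day 0 shift table would do so cheaply

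*SAP*

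**What the plan says.** The laboratory primary endpoint (SAP Amendment 2, 5.1; protocol 10.1) is "Occurrence of haematological and biochemical laboratory abnormalities, after vaccination, in all subjects, in all vaccine groups". The line beneath it specifies any abnormality on Days 7, 60, 67, 210 and 420.

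Two summaries are planned per parameter and group:

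- **By-visit table.** SAP 7.1.2: "The percentage of subjects having haematology and biochemistry results below or above the normal laboratory ranges will be tabulated by time point". SAP 7.2.2 and protocol 10.6.2 repeat it.
- **Maximum-grade table.** For the Day 90 analysis, "The maximum grading from Screening up to Visit 6 (Day 90) will be tabulated"; for the Day 420 analysis, "The maximum grading from Screening up to Visit 8 (Day 420) will be tabulated". The SAP adds: "Those laboratory parameters not included in the FDA grading scale will not be graded".

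Protocol 3.1 schedules safety blood samples from every subject at Screening and Day 0 as well as on the five post-vaccination days. For Step 2, protocol 4.3.2 warns that "various pre-existing laboratory abnormalities might be detected" and excludes only those the investigator judges clinically significant.

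The laboratory text contains no shift table, no denominator of subjects in range at Day 0 and no definition of a new abnormality. Baseline enters in two places only: the haemoglobin change-from-baseline grades in protocol Table 26, and protocol 8.1.4, under which clinically significant findings that worsen from baseline are reported as AEs or SAEs.

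**The concern.** The data are paired: each subject has a Day 0 result and up to five later ones. The by-visit table reduces them to one unlinked percentage per visit. A subject who is out of range at Day 0 and unchanged at Day 7 counts at Day 7 exactly as a newly abnormal subject does. A subject who becomes abnormal can be offset in the percentage by one who returns to normal.

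The maximum-grade table avoids the offsetting, because it takes each subject's worst value. Its window opens before vaccination, however, so it too mixes pre-existing with new abnormalities. It is also silent on what the scale does not grade. Of the parameters in protocol Table 9, RBC, basophils and monocytes have no grade in Table 26, and neutrophils, lymphocytes and platelets are graded for decreases only. For those parameters and directions the by-visit table is the only tabulated summary.

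At stake is whether a reader of a first-in-human safety report can tell, parameter by parameter, how many subjects became abnormal after vaccination.

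**Working it through.** **Inputs**

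- Step 2 group size: 30 (protocol 4.1).
- Out of range at Day 0: not given. Assumed 6/30 (20%), with range 3/30 to 9/30 (10% to 30%).
- Confidence intervals: exact (Clopper-Pearson), the method cited in SAP section 11.

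**The plan's own figure.** No figure is stated for the laboratory summary. The Step 2 detection figure in protocol 10.3 does reproduce: 1 − 0.95^30 = 0.7854, against the stated 78.5%.

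**Formulas.** For one parameter, one direction and one post-dose visit, let b be the number out of range at Day 0, r the number who resolve and c the number newly out of range.

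- By-visit table: (b − r + c)/30
- Newly out of range among those in range at Day 0: c/(30 − b)
- Maximum-grade table, treating every abnormality as gradable: (b + c)/30

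**Results with b = 6**

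| Case | r | c | By-visit table (95% CI) | Newly out of range (95% CI) | Maximum-grade table |
|---|---|---|---|---|---|
| A | 0 | 0 | 6/30 = 20.0% (7.7–38.6) | 0/24 = 0% (0–14.2) | 6/30 = 20% |
| B | 3 | 3 | 6/30 = 20.0% (7.7–38.6) | 3/24 = 12.5% (2.7–32.4) | 9/30 = 30% |
| C | 6 | 6 | 6/30 = 20.0% (7.7–38.6) | 6/24 = 25.0% (9.8–46.7) | 12/30 = 40% |

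The by-visit table cannot tell the three cases apart. The maximum-grade table moves with c, but it shows 6, 9 or 12 subjects where the new ones number 0, 3 or 6. Subtracting the Day 0 column from it would not reliably recover c: being out of range and being graded differ (for ALT and AST, Grade 1 starts at 1.1 × ULN), and Screening results also count.

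**Range over the assumption.** With an unchanged visit percentage, r = c, and c can be anything from 0 to b. The newly-out-of-range rate can then lie within:

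- b = 3: 0 to 3/27 = 11.1%
- b = 6: 0 to 6/24 = 25.0%
- b = 9: 0 to 9/21 = 42.9%

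These are bounds from counting. They need no assumption about within-subject correlation, and they do not say which value is likely.

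**The case against.** Several points on the other side stand.

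- **The endpoint wording.** A reader might infer that the by-visit table fails its own endpoint. It does not. The endpoint is spelled out as any abnormality on the listed days, and a percentage out of range on each day matches that.
- **Offsetting.** A reader might infer that new and resolving abnormalities cancel throughout the laboratory analysis. They cancel only in the by-visit table. For graded parameters and directions the maximum-grade table is a second summary without cancellation.
- **Placebo.** A reader might infer that vaccine effects are overstated. Randomisation is concurrent within each step and balances Day 0 abnormality in expectation, so a vaccine–placebo difference at a visit is not systematically inflated. The protection is partial: groups of 30 can differ by chance, SAP 7.1 and 7.2 pool placebo subjects aged 18–40 with smokers aged 50–70, and comparing group percentages still does not show within-subject change.
- **Power.** It is tempting to say that ignoring the pairing loses power. The laboratory analysis is descriptive and no test is planned, so no power claim applies.
- **Fluctuation.** New onset is not a clean vaccine signal either. With an assumed 20% prevalence, within-subject correlation 0.5 and no net change, 0.20 × 0.80 × (1 − 0.5) = 8% of subjects enter the abnormal range and 8% leave it. New onset would be 0.08/0.80 = 10%, or 2.4 of 24, from fluctuation alone. It must be read against placebo.
- **Other safeguards.** The internal Safety Review Committee reviews safety data unblinded (protocol 8.10.2), worsening judged clinically significant becomes an AE, and individual listings come with the final analysis. None of these is a tabulated summary of any abnormality relative to Day 0, and listings are not provided at the Day 90 analysis.
- **Table shells.** The TFL annex was not among the documents and could contain shift tables. The SAP text does not commit to them.

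**Conclusion.** The point holds as a cheap improvement. The planned tables report who is out of range at each visit and the worst grade since Screening. Haemoglobin change grades aside, they do not report who became abnormal relative to Day 0. With 6/30 assumed out of range at Day 0, a displayed 20% is compatible with 0% to 25% new onset; the upper bound runs from 11.1% to 42.9% as the assumed Day 0 count goes from 3 to 9.

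The size in practice depends on a Day 0 rate that the documents do not give. The protocol says only that pre-existing abnormalities might be detected, and only for Step 2; it does not predict that they will be common. Step 1 enrols healthy young adults, and borderline Screening results must be re-tested before Visit 1 (protocol 5.6.14.1). The documents do not support reading this as a defect that invalidates the safety analysis.

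**What to change.** In SAP 7.1.2 and 7.2.2, and in protocol 10.6.2 if it is amended:

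1. Keep the by-visit table as the summary of the stated endpoint.
2. For each parameter and post-vaccination visit, add a shift table of low/normal/high at Day 0 against low/normal/high at that visit, by group and including placebo. Use the Screening value if Day 0 is missing.
3. From it, report the percentage newly out of range in each direction among subjects not out of range in that direction at Day 0, with its exact 95% CI.
4. State that new onset is to be interpreted against the placebo group, because ordinary fluctuation also produces some new abnormalities.

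If the TFL annex already contains such tables, a sentence in the SAP referring to them is enough.

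The cost is SAP wording, programming and more table pages, using data already scheduled for collection. The denominator is smaller (24 instead of 30 in the illustration), so the intervals rest on fewer subjects.
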